Will pregnant women and/or fetuses (as described in 45 CFR 46 Subpart B) be enrolled in the research? No

E4. Neonates

Will neonates of uncertain viability or nonviable neonates (as described in 45 CFR 46 Subpart B) be enrolled in the research? No

E5. Children

Will children be enrolled in the research? No

Section F: Design/Procedure

F1. Design

Select one category that most adequately describes your research: c) Pilot

Discuss the research design including but not limited to such issues as: probability of group assignment, potential for subject to be randomized to placebo group, use of control subjects, etc.

Phase I: 20 subjects with COVID-19 infection that are being treated in the hospital. This means that this patient population is positive to COVID-19 and have been admitted with no more than 48 hours to the hospital due to severe infection. In some cases, the patients will not able to consent at the time of enrollment. This determines a high grade of severity of illness. Therefore, a family member/legal representative will be contacted via telephone for consenting. Participants will be randomized to intervention (IG) or control group (CG). The entire cohort will receive daily EE in lower extremity (e.g. Gastronemius, tibial anterior muscle) up to 1 hour. EE therapy will be provided using portable device. The EE device will be functional for IG and non-functional for CG. The duration of the study will be 2 weeks or until patient discharge, whichever comes first. The primary outcomes include between group difference and change from the baseline in muscle endurance, muscle strength, lower extremity tissue oxygen saturation, neuropathy, and muscle atrophy. Outcomes will be assessed at baseline, time of discharge or 2 weeks, whichever comes first. Due to the condition of the patient we are looking to reduce the interaction with staff, the device will be placed with no additional requirements. Physical therapy targets other physical performances, this device is aimed to improve blood flow, tissue perfusion and muscle activation while the patient is non-responsive to physical activities.

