P-values of 0.05 or less will be considered statistically significant based on a two-sided test unless otherwise noted. All variables will be tabulated descriptively at each scheduled time point (baseline and discharge date). For each continuous variable, the analyses will include the mean, standard deviation, minimum and maximum. For each categorical variable, the summary will include frequencies and percentages. Each variable will be analyzed using all available data. Baseline variables will be summarized using descriptive statistics. We assume that a successful intervention is also helpful to maintain subjects muscle mass, reduce neuromyopathy signs and increase venous return flow. The measured parameters (e.g. muscle circumference, sEMG, kent imaging, doppler, etc.) should change substantially from baseline to the end of the intervention. For example, the EMG amplitude values should show increased voltages. Next, for all continuous variables, pre-treatment scores will be regressed on post-treatment scores to form residualized change scores (e.g. sEMG, VPT, dynamometer, etc). Correlations will then be generated among these scores to determine whether changes in sEMG factors are related appropriately with increases in (clinically assessed) functional capacities and self-report measures of activities. ANOVA test will be used to examine significant difference between patients with severe risk factors for prolonged ICU stage (e.g. age, BMI, cardiovascular morbidities). Moderator effects will also be examined for exploratory purposes. Using gender as an example, mixed design ANOVAs will be conducted to determine whether mobility factors change over the course of treatment at different rates or with different patterns for men and women. Additional analyses will test whether changes in muscle strenght and neuropathy (e.g. VPT and dynamometer assessement at time of discharge).

Section H: Potential Risks/Discomforts

H1. Potential Risks/Discomforts

Describe and assess any potential risks/discomforts; (physical, psychological, social, legal, or other) and assess the likelihood and seriousness of such risks:

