activation. The device is used to reduce pain. However, the proposed treatment may assist in preventing or improving hospital-acquired Weakness because of prolonged hospital stay . In addition, the participation in this study may help the investigators better understand how COVID19 may impact cause myopathy and neuropathy and how to best help these patients to recover from prolonged hospital-stay .

Primary outcomes include neuropathy (assessed using VPT test); muscle function (assessed using sEMG), and tissue oxygenation (assessed using Kent Imaging). Secondary outcomes include weakness (assessed using dynamometer); muscle atrophy (assessed by weight loss as well as measuring ankle, calf, and thigh circumference); venous return flow (Doppler US [optional]); frailty (frailtymeter [optiona]); hospital length of stay (patient medical record); and major adverse events (patient health record). The primary and secondary outcomes will be assessed at baseline (if feasible) and on biweekly basis up to 4 weeks or hospital discharge, whichever came first. Appropriate mixed models (linear for continuous or Generalized Estimating Equations (GEEs) for non-continuous or non-parametric variables) will be used to test the intervention effect for each of the primary (e.g., tissue perfusion, tissue oxygen delivery, neuropathy severity, and myopathy incident) or secondary (e.g., frailty, weight loss, MAE, etc) outcomes.

Also, participation may help the investigators design a practical assessing method to identify the impact of neuromyopathy in the hospital setting. This may allow physicians to provide personalized care by monitoring muscle loss and limb complications caused by prolonged hospital length of stay.

Describe potential benefit(s) to society of the planned work.

As described above, this type of work may allow physicians to provide more personalized care for hospitalized patients in need of physical therapy for continuous and prolonged periods, specially when having a severe illness that includes medical staff risk contact.

Do anticipated benefits outweigh potential risks? Discuss the risk-to-benefit ratio.

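### Section G2 calls any outcome with p≤0.05 statistically significant, with five primary outcomes per phase (three in Section I) and no rule for error across them

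*Combined protocol and SAP*

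**What the plan says.** Section G2 (Data Analysis) gives the only error rate in the document: "P-values of 0.05 or less will be considered statistically significant based on a two-sided test unless otherwise noted". No exception is noted elsewhere. The G2 form asks which analysis is primary, and the answer names none.

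Section I (Potential Benefits) says that mixed models or GEEs "will be used to test the intervention effect for each of the primary" and secondary outcomes. That is separate testing of each outcome.

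The primary outcomes are listed in more than one way:

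- Section F1 gives the same five for Phase I and Phase II: "between group difference and change from the baseline in muscle endurance, muscle strength, lower extremity tissue oxygen saturation, neuropathy, and muscle atrophy".
- Section I gives three, tied to neither phase by name: "Primary outcomes include neuropathy (assessed using VPT test); muscle function (assessed using sEMG), and tissue oxygenation (assessed using Kent Imaging".
- The model sentence in Section I gives four as examples: "tissue perfusion, tissue oxygen delivery, neuropathy severity, and myopathy incident".

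The document contains no hierarchy, composite, multiplicity adjustment or requirement that all primary outcomes succeed. The only outcome-related analyses that G2 marks as exploratory are the moderator analyses: "Moderator effects will also be examined for exploratory purposes".

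**The concern.** The study is a pilot, but part of its stated purpose is proof-of-concept effectiveness, and Aim 2 of Phase I is to examine effectiveness. With several primary outcomes each tested at 5%, one small p-value among them can be reported, under the plan's own wording, as a statistically significant effect of stimulation. With an ineffective device, that happens in a phase more often than the 5% that applies to any single test. Nothing tells the analyst or the reader how to interpret one positive outcome among several null ones.

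Reconciling the outcome lists would not remove the problem. Whether three or five outcomes are kept, each is still tested at the full 5%.

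**Working it through.** **Figure to reproduce.** There is none. The 0.05 is a chosen threshold, and G1 describes 40 subjects as a convenience sample without power inputs.

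**Inputs from the document**

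- Per-test two-sided level: 0.05 (G2).
- Primary outcomes per phase: k = 5 (F1, both phases) or k = 3 (Section I).
- Phase II arms: 10 and 10 (F2). Phase I: 20 randomised, ratio not stated (F1).

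**Assumptions**

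- Phase I is also 10 v 10.
- There is one between-group test per primary outcome.
- Two-sample t tests stand in for the planned mixed models or GEEs.
- All pairs of outcomes share one correlation. The document gives none, so a range is shown.

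**Independent outcomes, no true effect.** P(at least one p≤0.05) = 1 − 0.95^k.

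- k = 3: 1 − 0.95³ = 1 − 0.857 = 14.3%.
- k = 5: 1 − 0.95⁵ = 1 − 0.774 = 22.6%.

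**Correlated outcomes.** Simulated two-sample t tests, 10 v 10, no true effect:

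| Correlation | 3 outcomes | 5 outcomes |
|---|---|---|
| 0 | 14% | 23% |
| 0.5 | 13% | 19% |
| 0.7 | 11% | 15% |
| 0.9 | 9% | 11% |

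A large-sample normal simulation agrees closely. At correlation 0.7 it gives 10.9% and 14.9%; at 0.9 it gives 8.4% and 10.1%.

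**Effect of Holm.** With no true effect, an error occurs only if the smallest p-value is at or below 0.05/k. For independent outcomes:

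- k = 3: 1 − (1 − 0.0167)³ = 4.92%.
- k = 5: 1 − (1 − 0.01)⁵ = 4.90%.

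Positive correlation lowers both.

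**Cost of Holm.** The difference detectable with 80% power, 10 v 10, comes from the noncentral t distribution with 18 degrees of freedom and noncentrality d × √(10/2), where d is in SD units:

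| Level | Where it applies | Detectable difference | Power at 1.32 SD |
|---|---|---|---|
| 0.05 | unadjusted | 1.32 SD | 80% |
| 0.0167 | first Holm step, 3 outcomes | 1.57 SD | 63% |
| 0.01 | first Holm step, 5 outcomes | 1.69 SD | 54% |

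**The case against.** The strongest case against the point is that this is a pilot with a convenience sample and no power claim. Many such studies reasonably leave outcome tests unadjusted, and forcing Holm on 10 v 10 loses a good deal of power. **This stands as an argument against mandatory adjustment.** It does not support G2 as written, because a pilot that leaves its tests unadjusted should call them exploratory. This plan adopts a significance threshold and reserves that label for moderator effects.

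A second objection is that nowhere does the plan say the trial succeeds if any one primary outcome is positive. G2 in fact describes a successful intervention as a joint pattern: muscle mass kept, neuromyopathy signs reduced, venous return increased. **This stands in part.** The plan has no formal win-on-any rule. But the sentence in G2 is introduced as an assumption about what success would look like, and it does not restrict when a single outcome may be called significant.

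A reader might infer more than the document supports:

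- **That a promised overall 5% is broken.** The 5% is a per-test rate, and no familywise rate is stated.
- **That both phases should be pooled into one error rate.** They study different populations and questions (prevention in hospital, recovery at home), and no section combines them into one claim.
- **That every Section I secondary outcome adds a test in each phase.** Length of hospital stay does not apply to Phase II outpatients, the Phase II assessments in F2 do not list Doppler, and Section I marks Doppler and frailty as optional.
- **That three primary outcomes is a phase-specific count.** Both phase-specific lists in F1 have five. The three come from a conflicting list in Section I.

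In the other direction, F1 defines the primary outcomes by both a between-group difference and a change from baseline: "The primary outcomes include between group difference and change from the baseline in" five measures. Counting one test per outcome may therefore understate the number of tests.

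**Conclusion.** The point holds as a gap in how results may be claimed. As written, the plan allows one chance result among several primary outcomes to be called statistically significant, and gives no guidance on reading it.

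With no true effect, the chance of at least one such result per phase is about 23% for five outcomes (14% for three) if they are independent. It falls to 11% (9%) at correlation 0.9. Every value in the range exceeds the 5% of a single test, by a factor of roughly two to four and a half. The size depends on the unstated correlations, on 10 v 10 in Phase I, and on t tests in place of the planned models.

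The pilot status limits the consequence, so this is an inexpensive improvement in wording. It is not a flaw that invalidates the design.

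**What to change.** **Preferred.** In G2, remove the significance rule for the outcome comparisons. Report every primary and secondary outcome as an IG minus CG difference with a 95% confidence interval, labelled exploratory or proof of concept. State that no claim of effectiveness will rest on a single p≤0.05. This needs only a change of wording; the cost is giving up the words statistically significant.

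**If the sponsor wants to keep a significance claim.** Two steps must come first: reconcile the primary outcome lists in F1 and Section I, and fix one between-group comparison per outcome. Then apply Holm to those p-values within each phase, reserve statistical significance for a Holm-adjusted p≤0.05, and report secondary outcomes as exploratory intervals. This involves more than G2. The difference detectable at the first step with 80% power rises from 1.32 SD to 1.57 SD with three outcomes or 1.69 SD with five.

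Neither option changes the sample size, visits or assessments.

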Physical Activity Monitoring: The subject will be given a wearable device (PAMSys) or a smart watch, that will be measuring several parameters including number of steps taken, duration of sitting, standing, walking and lying, time taken and number of transitions from sit to stand, and walking speed for 48 hours. At the end of the specific visit, the subject will be given the device, if they are given PAMSys it will be attached to pendant to wear around the neck, otherwise they may wear the smart watch on their wrist. Investigators will provide a pre-paid envelope where the subject may place the device and send back it to the investigating team.

Oxygen Level Assessment: Oxygen saturation will be measured using a pulse oximeter.

The supervision of this study will be by pulmonary care specialists, and the location will be at Baylor College of Medicine McNair Campus.

Section G: Sample Size/Data Analysis

G1. Sample Size

How many subjects (or specimens, or charts) will be used in this study? Local: 40 Worldwide: 40

Please indicate why you chose the sample size proposed:

Sample size is convenient and selected based on available resources to demonstrate feasibility and the proof of concept effectiveness of EE therapy for COVID-19 patients admitted to ICU and post-ICU. We plan to recruit 40 eligible subjects.

G2. Data Analysis

Provide a description of your plan for data analysis. State the types of comparisons you plan (e.g. comparison of means, comparison of proportions, regressions, analysis of variance). Which is the PRIMARY comparison/analysis? How will the analyses proposed relate to the primary purposes of your study?

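### G2 names no primary comparison and has no complete sentence comparing IG with CG; the intervention-effect test sits in Section I, with a primary outcome list that conflicts with F1

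*Combined protocol and SAP*

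**What the plan says.** **G2 (Data Analysis).** The form's prompt includes "Which is the PRIMARY comparison/analysis". The answer sets a two-sided 0.05 threshold and then describes:

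- Descriptive tables: "All variables will be tabulated descriptively at each scheduled time point (baseline and discharge date".
- An expectation of success. It assumes that "a successful intervention is also helpful to maintain subjects muscle mass", and continues: "The measured parameters (e.g. muscle circumference, sEMG, kent imaging, doppler, etc.) should change substantially from baseline to the end of the intervention".
- Residualized change scores, whose stated use is "Correlations will then be generated among these scores".
- An ANOVA by patient risk factors, and mixed-design ANOVAs for moderators, with gender as the example.
- A last sentence on strength and neuropathy that breaks off before saying what is compared.

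**F1 (Design), both phases.** Patients are randomized to a functional (IG) or non-functional (CG) device. "The primary outcomes include between group difference and change from the baseline in muscle endurance", followed by strength, tissue oxygen saturation, neuropathy and atrophy. For Phase I, "Outcomes will be assessed at baseline, time of discharge or 2 weeks, whichever comes first". F2 (Phase I, Aim 2) gives the same time point for neuropathy and myopathy incidence.

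**Section I (Potential Benefits).** The primary outcomes are neuropathy by VPT, muscle function by sEMG and tissue oxygenation by Kent Imaging. Weakness and atrophy are secondary. Baseline is taken if feasible, then assessment is biweekly up to 4 weeks or discharge. Linear mixed models or GEE test the intervention effect. The sentence on these models gives perfusion, oxygen delivery, neuropathy severity and incident myopathy as examples of primary outcomes.

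**The concern.** The section that should define the randomized comparison does not contain it, and the section that contains a test does not agree with the design section on what is primary. Three choices therefore stay open until data are seen: which outcomes carry the claim, at which time point, and how baseline enters.

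The pre-post expectation is a problem of its own. Phase I is preventive, so benefit on muscle mass would show as less loss than in controls, not as a substantial change from baseline. In Phase II, patients recovering from COVID-19 may improve without the device. Because F1 puts between-group difference and change from baseline on the same footing, an improvement within the IG arm alone could be reported as a primary result.

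**Working it through.** **1. Does G2 contain an IG-versus-CG comparison?** Taking each analysis in turn:

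| G2 element | What is compared |
|---|---|
| Descriptive tables | Nothing tested |
| Expected change from baseline | Before against after; no control reference |
| Residualized change scores | Correlations among outcomes |
| ANOVA | Patient risk factors |
| Mixed-design ANOVA | Moderators, e.g. men and women, over time |
| Last sentence | Unfinished; comparator unknown |

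No complete sentence compares the arms, and none is called primary.

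**2. Do the primary outcomes agree?**

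| Outcome | F1 | Section I list | Section I model examples |
|---|---|---|---|
| Neuropathy | primary | primary | primary |
| Tissue oxygenation | primary | primary | primary (oxygen delivery) |
| Strength / weakness | primary | secondary | not named |
| Atrophy | primary | secondary | weight loss named as secondary |
| Endurance | primary | not named | not named |
| sEMG muscle function | not named | primary | not named |
| Perfusion | not named | not named | primary |
| Incident myopathy | not named | not named | primary |

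Only neuropathy and tissue oxygenation are primary throughout. F2 (Phase I, Aim 2) assesses myopathy partly by calf size and weight change, which Section I counts among its secondary atrophy measures.

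**3. Timing.** F1 and F2 put the Phase I assessment at discharge or 2 weeks. Section I gives a biweekly schedule up to 4 weeks or discharge and names no phase. G2 tabulates at baseline and discharge date, which has no meaning in outpatient Phase II with its weekly clinic visits.

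**4. False positives across primaries.** The plan gives alpha 0.05 two-sided and no multiplicity rule. Assume one test per outcome, independent outcomes and no true effect. The chance of at least one p ≤ 0.05 is 1 − 0.95^k:

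- F1, k = 5: 1 − 0.95^5 = 1 − 0.7738 = 22.6%.
- Section I, k = 3: 1 − 0.95^3 = 1 − 0.8574 = 14.3%.

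**5. Effect of baseline handling on precision.** The plan gives no SD, effect size or power, so it has no figure to reproduce beyond 20 + 20 = 40. F2 states 10 per arm for Phase II; it is assumed for Phase I. The unit is the SD of the final value, and r is the assumed pre-post correlation.

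- Unadjusted, mean 95% half-width = t(18) × √(2/10) × E[s] = 2.101 × 0.447 × 0.986 = 0.93 SD.
- ANCOVA, all baselines present = t(17) × √(2/10) × E[s] × √(1 − r²) × 1.030, where 1.030 is the mean cost of chance baseline imbalance. The constant part is 2.110 × 0.447 × 0.985 × 1.030 = 0.957.
  - r = 0.3: 0.957 × 0.954 = 0.91 SD
  - r = 0.5: 0.957 × 0.866 = 0.83 SD
  - r = 0.7: 0.957 × 0.714 = 0.68 SD

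**6. Why a within-arm change is not evidence of a device effect.** Assume both arms drift by 0.5 SD of the change score and the device does nothing. A paired t-test in one arm of 10 has noncentrality 0.5 × √10 = 1.58 and critical value 2.262 on 9 df. It is significant in the direction of the drift in about 29% of trials.

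**The case against.** **The contrast is clearly intended.** Patients are randomized, F1 names the between-group difference, and Section I names models for the intervention effect. This stands. A reader might infer that the trial has no between-group analysis, or that success is formally defined as pre-post change; the documents support neither. The defect is that G2 lacks the analysis and that nothing ranks it above change from baseline.

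**G2's last sentence may have held the comparison.** Its ending is missing, by authoring or by extraction. The claim is therefore limited to complete sentences.

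**Baseline may already be handled.** Section I measures outcomes at baseline and later and then fits mixed models, so baseline as a repeated response is a possible reading. It would be too strong to say that the plan ignores baseline; it does not state how baseline enters. The unadjusted 0.93 SD is thus a reference point, not the plan's declared analysis.

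**Timing may be compatible.** Read as every two weeks, Section I's schedule gives week 2 for Phase I and week 4 for Phase II. A flat contradiction on Phase I timing is a tempting inference, but the text supports only ambiguity.

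**sEMG may be the endurance measure.** H1 says that EMG detects fatigue. No section makes the link to endurance, and the strength and atrophy conflict remains either way.

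**It is a pilot with a convenience sample.** This lowers the stakes. But the plan tests at p ≤ 0.05 and aims at proof-of-concept effectiveness, so the comparison needs defining in advance.

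**Conclusion.** The point holds and should be fixed. G2 leaves the question about the primary comparison unanswered, no complete sentence in it compares IG with CG, and the primary lists in F1 and Section I cannot both be followed. The missing primary contrast and the conflicting lists are certain from the text. Phase I timing and baseline handling are unclear rather than wrong.

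The sizes are illustrations. The 22.6% and 14.3% assume independent outcomes with one unadjusted test each; positive correlation would lower them. They do not count the further freedom to choose between lists. The half-widths assume 10 per arm, complete baselines and the stated correlations. The gain from adjustment is minor at r = 0.3 (0.91 against 0.93 SD) and substantial at r = 0.7 (0.68 SD). The 29% rests on an assumed drift.

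**What to change.** **In G2**, bring in the Section I test and state:

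- The primary analysis in each phase is the IG minus CG difference with 95% CI at the final randomized assessment. For Phase I this is discharge or 2 weeks, whichever comes first. For Phase II it is week 4, before any control patient switches to an active device.
- Continuous outcomes: a linear mixed model with the baseline and all scheduled randomized post-baseline values as responses, including Phase II visits 1 to 3. It has a common baseline mean, a group-by-time term and a small-sample (t-based) reference. Patients without a baseline value stay in.
- Baseline and final values are those taken before that visit's stimulation, since F2 includes one hour of stimulation at the Phase II baseline and week-4 visits. Because F2 measures both legs in Phase I, the two legs are averaged or modelled within patient.
- Binary outcomes: the risk difference with a small-sample method that still gives an interval when an arm has no events.
- Within-arm changes are descriptive.

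Replace the expectation of substantial change with an expected IG-versus-CG direction for each measure, for example less loss of circumference in IG than in CG in Phase I.

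**In F1**, reword the primary outcomes as the between-group difference in change from baseline.

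**Across F1, G2 and Section I**, use one primary list and one assessment schedule per phase. Neuropathy and tissue oxygenation are common ground. The sponsor decides on the rest, and says whether p-values across primaries are adjusted or descriptive.

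**Cost.** Wording only, with no new outcome measures or visits. Improvement within the IG arm alone can no longer be claimed as success, and the precision gain is small if the pre-post correlation is low.

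### Section G2 forms the residualized change scores backwards (pre regressed on post), so the sEMG–function correlations mix baseline association into what is read as association of changes

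*Combined protocol and SAP*

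**What the plan says.** Section G2 of the combined protocol and SAP sets a rule for every continuous variable, naming sEMG, VPT and the dynamometer as examples: "pre-treatment scores will be regressed on post-treatment scores to form residualized change scores". The next sentence gives the use: "Correlations will then be generated among these scores to determine whether changes in sEMG factors are related appropriately with increases in (clinically assessed) functional capacities". Self-reported activity is to be examined in the same way. The significance rule opens the same section: "P-values of 0.05 or less will be considered statistically significant based on a two-sided test unless otherwise noted".

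No other section restates or corrects the direction of this regression. The treatment comparison is described in Section I (Potential Benefits), where linear mixed models or GEE "will be used to test the intervention effect for each of the primary" and secondary outcomes. The moderator analyses in G2 are mixed-design ANOVAs. Neither is said to use the residualized scores.

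On size, G1 says "We plan to recruit 40 eligible subjects", a convenience sample. F1 and F2 put 20 in each phase.

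**The concern.** When Y is regressed on X, Y is the outcome and X the predictor. A residualized change score is what remains of the post-treatment value once baseline has been used to predict it. That requires post on pre, and G2 says the reverse. The residual it describes is the part of the baseline value that the follow-up value does not predict. It is uncorrelated with the post-treatment value, strongly correlated with baseline, and negatively correlated with raw change. It still carries information on change, but mixed with baseline level and with the sign reversed.

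Two such scores can correlate simply because sEMG and strength go together at admission or at the first clinic visit, even if their changes are unrelated. Conversely, a real link between changes can be diluted until it is missed. This is the only analysis in the plan that asks whether sEMG change tracks functional change, and Section I makes muscle function by sEMG a primary outcome.

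**Working it through.** **Inputs from the documents.** Direction: pre regressed on post (G2). Test: two-sided, 0.05 (G2). n = 20 per phase (F1, F2) and 40 in total (G1).

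**Inputs assumed, because the documents give none.** r is the pre-post correlation, taken as equal in both measures. c₀ is the correlation of the two baselines. cₑ is the correlation of the two baseline-adjusted changes. The baseline of one measure is taken as unrelated to the adjusted change in the other.

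**Model.** For each standardized measure, post = r·pre + √(1 − r²)·e, with e independent of pre.

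**Score in the usual direction.** post − r·pre = √(1 − r²)·e. Two such scores correlate cₑ, whatever c₀ is.

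**Score as written.** pre − r·post = (1 − r²)·pre − r√(1 − r²)·e. Dividing by its SD, √(1 − r²), gives √(1 − r²)·pre − r·e. Therefore:

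- its correlation with baseline is √(1 − r²) = 0.95, 0.87, 0.71 at r = 0.3, 0.5, 0.7;
- its correlation with raw change is −0.81, −0.87, −0.92 at the same r;
- two such scores correlate **(1 − r²)·c₀ + r²·cₑ**.

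The two sign reversals cancel within a pair of these scores. They would not cancel if one score were read alone or paired with a variable formed differently.

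The weights on c₀ and cₑ are equal when r² = 0.5, that is r = 0.71. Expected correlations by the formula:

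| r | weight on c₀ | c₀ = 0.5, cₑ = 0 | c₀ = 0, cₑ = 0.5 | c₀ = 0.3, cₑ = 0.5 |
|---|---|---|---|---|
| 0.3 | 0.91 | 0.455 | 0.045 | 0.318 |
| 0.5 | 0.75 | 0.375 | 0.125 | 0.350 |
| 0.7 | 0.51 | 0.255 | 0.245 | 0.398 |
| 0.9 | 0.19 | 0.095 | 0.405 | 0.462 |
| correct direction | 0 | 0 | 0.5 | 0.5 |

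**Rejection rates.** These come from simulation with residuals estimated in each sample, a two-sided Pearson test at 0.05 and 40,000 replicates per setting. Repeat runs agreed within about one percentage point. At n = 20:

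| Setting | r = 0.3 | 0.5 | 0.7 | 0.9 | Correct direction |
|---|---|---|---|---|---|
| (a) c₀ = 0.5, cₑ = 0 (false positives) | 49% | 34% | 16% | 6% | 5% |
| (a′) c₀ = 0.3, cₑ = 0 (false positives) | 20% | 14% | 9% | 5% | 5% |
| (b) c₀ = 0, cₑ = 0.5 (power) | 5% | 7% | 15% | 39% | about 58% |
| (c) c₀ = 0.3, cₑ = 0.5 (power) | 26% | 31% | 39% | 51% | about 59% |
| (d) c₀ = cₑ = 0.5 (power) | about 60% | about 60% | about 60% | about 60% | about 60% |

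The mean sample correlation in (a) was 0.42, 0.35, 0.24 and 0.09, slightly below the formula, as expected at n = 20. If both phases were pooled (n = 40), (a) would become 84%, 66%, 34% and 8%.

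**Unequal r.** With pre-post correlations r₁ and r₂, the expected correlation is √((1 − r₁²)(1 − r₂²))·c₀ + r₁r₂·cₑ. For r₁ = 0.3, r₂ = 0.9 and c₀ = cₑ = 0.5 this is 0.5 × (√(0.91 × 0.19) + 0.27) = 0.5 × 0.686 = 0.34, against 0.5. The absence of distortion in (d) therefore depends on equal r.

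**The case against.** **It is probably a slip.** The clause names its product as residualized change scores, and the next sentence reads them as changes and increases. Both point to post on pre, and G2 is loosely written elsewhere (its last sentence has no predicate). This is fair: that the text is reversed is certain, that the analysis will be distorted is not. But nothing in the documents gives the right direction, and an analyst following G2 literally would compute the wrong residual.

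**It is peripheral.** These are supportive correlations in a pilot with a convenience sample, and no listed outcome is a correlation of changes. This stands. It limits the severity but does not make the rule right.

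**The largest figures come from extreme settings.** Settings (a) and (b) each set one association to zero. With c₀ = 0.5 and cₑ = 0.4, rejection at n = 20 is 49% as written against 40% at r = 0.7, and 43% against 39% at r = 0.9. This stands too: (a) and (b) are illustrations at the extremes, not expected values.

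**Pooling to n = 40 is not stated.** No section pools the phases for this analysis, and F2 lists questionnaires only for Phase II visits. The n = 40 figures are conditional, and n = 20 is the better guide.

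**The 5% reference ignores treatment arm.** If arms are combined and treatment shifts both measures by 1 residual SD, correctly formed scores with no within-arm link still reject about 13% of the time at n = 20. This is a separate limitation of the planned correlations. Reversing the regression does not cure it, and it does not justify the backward direction.

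**Conclusion.** The concern holds. As written, G2 builds the score in the wrong direction, and correlations among these scores do not answer the question the plan puts to them. The size depends on three correlations that the documents do not give. At n = 20 the effect runs from none (equal associations and equal r), through small (r near 0.9), to a false-positive rate of 49% or power of 5% in the least favourable settings shown. Below r of about 0.71 the result reflects baseline association more than change.

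The damage is confined to the sEMG–function and self-report correlations. The mixed models and GEE for the intervention effect, and the moderator ANOVAs, are not affected as described. This should be fixed before analysis, but it does not threaten the treatment comparison.

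**What to change.** In G2, reverse the clause, for example: *For each continuous variable, the post-treatment score will be regressed on the pre-treatment score, and the residual will be used as the residualized change score.* Add one sentence confining these scores to the correlations between change in sEMG and change in functional or self-report measures. The sentence that follows in G2 already implies this, so the addition is for clarity only.

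The cost is one corrected clause and one short sentence. No data, visits or patients are added.
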